#### 4.4 Information on study drug

## 4.4.1 Methotrexate (MTX)

Nonproprietary name:	Methotrexate
Brand name:	Rheumatrex ® , etc.
Dosage form/Dosage:	Capsules/Tablets, 2 mg/2.5 mg

Pharmacokinetics:

The maximum blood MTX concentration was in 1 to 2 hours postdose among 17 RA patients orally receiving MTX 6 mg/week for 12 weeks. MTX binds with albumin by 53% to 60% in the serum. Meanwhile, the MTX concentration in the erythrocyte remains the same throughout treatment with MTX even if the serum concentration is low. There are 3

known metabolic pathways in human, including that by which it is metabolized to 7-OH-MTX by aldehyde oxidase in the liver, that by which it is metabolized to MTX-PG via polyglutamate in the liver or erythrocyte, and that by which it is metabolized to APA by carboxy peptidase in enteric bacteria.

Characteristics and action mechanism of the drug:

MTX is an antifolic drug synthesized for the first time in 1947, and acts on DHFR which produces active folic acid necessary for nucleic acid synthesis, and inhibits thymidylate synthesis and purine synthesis to obstruct cellular proliferation. It has an immunosuppressive and anti-inflammatory effects against T cell, B cell, macrophage, neutrophil, vascular endothelial cell, and fibroblast cell, and by which, is thought to provide its antirheumatic action. Basically, it should be administered via weekly intermittent dose.

Application to autoimmune disease:

Upon synthesis in 1947, it was widely used for treatment of various types of malignant tumor, and then, later confirmed to have an efficacy for rheumatoid arthritis, and then, approved in 1988 in the U.S. as an antirheumatic drug. Thereafter, MTX was confirmed to have an effect to prevent progression of osteoclasis and to improve vital prognosis, and became a first-line drug for treatment of RA. In Japan, it was approved in 1999 after completion of phase III study. The maximum dose in Japan is about half of the standard dose used overseas, and was approved in February 2011 through an application for partial change in the authorization status, and a dosage up to 16 mg/week was allowed for use. Also, its efficacy in combination use with bDMARDs has been demonstrated; to date, it is still an anchor drug of RA treatment.

Main ADRs (serious ADRs and other relevant reactions: Rheumatrex® Package Insert, version 20):

Shock/anaphylaxis, bone marrow depression, infection, tuberculosis, fulminant hepatitis/hepatic failure, acute renal failure/tubular necrosis/severe nephropathy, interstitial pneumonia/pulmonary fibrosis/pleural effusion, toxic epidermal necrolysis (TEN)/oculomucocutaneous syndrome (Stevens-Johnson syndrome), hemorrhagic enterocolitis/necrotising enterocolitis, pancreatitis, osteoporosis, cerebropathy (including leukoencephalopathy), and lymphoproliferative disorder

## 4.4.2 Adalimumab (ADA)

Nonproprietary name:	Adalimumab (recombinant)
Brand name:	Humira ®
Dosage form/Dosage:	Syringe/Pen, 40 mg

Pharmacokinetics:

The serum drug concentration increased dose-proportionally in subjects receiving a single dose of 20, 40, 80 mg;  $T_{max}$  was 204 hours in the 40 mg group, and its half-life was 298.0 hours. The steady-state trough concentration of ADA was about 3 µg/mL in Japanese RA patients subcutaneously receiving ADA 40 mg every other week. It is a human IgG, and like the intrinsic immunoglobulin metabolic process, is taken into the reticular system, and assumed to be broken down to its components, amino-acid and glucose in the endosome.

Characteristics and action mechanism of the drug:

It is the world's first human anti-human TNF $\alpha$  monoclonal antibody that neutralizes TNF $\alpha$ , which is a cytokine that involves in inflammatory response and immune reaction, and by which, reduces the concentration of TNF $\alpha$ .

Application to autoimmune disease:

It was approved in December 2002 in the U.S., and in September 2003 in EU. In Japan, the dosage of MTX in combination use was different from that in the development programs in the U.S. and Europe, and therefore, an ADA monotherapy study was conducted in Japan, and the efficacy and safety similar to Western RA patients were confirmed in Japanese RA patients, and upon which, it was approved in April 2008. Also, a clinical study was conducted in RA patients previously untreated with MTX or leflunomide and whose duration of disease was within 2 years, and in which, its efficacy in preventing progress of joint destruction was confirmed; upon which, the indication, "Rheumatoid arthritis (including prevention of structural joint injury)" was approved in August 2012.

Key ADRs (serious ADRs: Humira® Package Insert, version 30): Serious infections such as sepsis/pneumonia, tuberculosis, Lupus-like syndrome, demyelinating disease, serious allergy, serious hematologic disorders (pancytopenia/thrombocytopenia/leukopenia/granulocytopenia), interstitial pneumonia, and hepatitis fulminant/hepatic impairment/jaundice/hepatic failure

#### 4.5 Study period

This study will be started upon the approval in each study site. The total study duration is assumed to be 4 years and 4 months, and the study is scheduled to be completed in June 2022.

Enrollment period:	March 2018 to July 2020 (2 years			
	and 5 months)			
Intervention period:	48 weeks			
Data collection, analysis, and report genera	tion periods: 1 year			
Total study period:	4 years and 4 months			

#### 4.6 Study interruption/discontinuation

The withdrawal criteria for individual subject are as shown in 5.3.

The entire study will be discontinued if either of the below criteria is met. The Lead Principal Investigator shall notify the principal investigator of each study site promptly upon her decision to discontinue the study. Then, each principal investigator shall promptly notify his/her subjects, and provide appropriate medical intervention and take other necessary actions.

- 1) Certified Review Board which the Lead Principal Investigator request to review recommends not to continue the study.
- 2) There is a safety concern that prevents this study from continuing further.
- 3) The Lead Principal Investigator judges that the entire study should be discontinued.

## 4.7 Management of study drug

Study drug will be obtained and controlled in accordance with each country's relevant regulations.

In Japan, the study drug will be used within the scope of the healthcare insurance; accordingly, subjects will obtain and use study drugs available in the market through pharmacies.

## 4.8 Storage of randomization code, and unblinding process

Randomization code for this study will be retained in the IWRS system. This is not a blinded study, and therefore, no unblinding process will be specified.

## 4.9 Specification of source data

All of the data recorded in EDC must be consistent with the source materials. Source materials are defined as documents, data, and records that were documented for the first time, such as subjects' informed consent form, medical record (clinical chart), clinical laboratory data, ECG data, and X-ray data.

If the following information is not provided in medical or other record, EDC will be considered as the source data.

- Status of study drug administration (e.g., reason for treatment discontinuation, reason for dose modification, etc.)
- Reason for using concomitant therapy (including drugs and non-drug therapies)
- Information concerning study discontinuation (e.g., lost to follow)
- Information concerning AEs (e.g., severity, causality, outcomes, etc.)

## 5 Inclusion/exclusion/withdrawal criteria

RA patients meeting all of the following inclusion criteria and not applicable to any of the following exclusion criteria will be eligible for this study.

## 5.1 Inclusion criteria

- 1) Patients aged  $\geq 18$  years ( $\geq 20$  years in Taiwan) at the time of informed consent
- 2) Patients who meet the 1987 revised ACR criteria or 2010 ACR/EULAR criteria

- 3) Patients who have RA within 2 years from initial diagnosis to informed consent
- 4) Patients who were previously untreated with MTX, JAK inhibitor, or bDMARDs
- 5) Patients who have disease activity of SDAI >11 at screening
- 6) Patients who are no need for concomitant use of DMARDs other than study drugs and hydroxychloroquine (only in South Korea and Taiwan) during the study as judged by principal investigator/sub-investigator at screening
- Patients who are no need for concomitant use of corticoid steroid equivalent to >10 mg/day prednisolone during the study as judged by principal investigator/subinvestigator at screening.
- 8) Female of child-bearing potential who can use appropriate contraceptive during the study, female in whom time from menopause to informed consent is ≥1 year, or female of no child-bearing potential through sterilization (bilateral tubal ligation, bilateral ovariectomy or hysterectomy, etc.)
- 9) Virile male who can use appropriate contraceptive during the study
- 10) Patients who can adequately understand this study procedures, and voluntarily consent in writing to take part in this study
   (consent of a legally-acceptable representative is also required for patients aged <20 years in Japan and aged <19 years in South Korea)

## 5.2 Exclusion criteria

- 1) Patients who currently have a malignant tumor, except for non-melanoma forms of skin cancer limited within epidermis, and uterine cervix cancer limited within epidermis
- 2) Patients who have serious infections such as sepsis
- 3) Patients who have active tuberculosis
- 4) Patients who have a history or current complication of demyelinating disease such as multiple sclerosis
- 5) Patients who have congestive heart failure
- 6) Pregnant female, or female who intend to conceive during the study period
- 7) Patients who have bone marrow depression and whom investigator considered ineligible
- 8) Patients who have chronic liver disease and whom investigator considered ineligible, or who is positive for HBs antigen
- 9) Patients who have nephropathy and whom investigator considered ineligible
- 10) Lactating female
- 11) Patients who have pleural effusion or ascites
- 12) Patients with a known hypersensitivity to MTX or ADA
- 13) Patients otherwise whom principal investigator/sub-investigator considered medically ineligible to participate in the study

## 5.3 Withdrawal criteria

Subjects should be withdrawn from this study if applicable to any of the discontinuation criteria presented below. Upon withdrawal, subjects should undergo assessments and tests for early termination. Also, the reason for withdrawal should be as necessary explained to the subject, and treatment after withdrawal should be given in a faithful manner to ensure there will be no disadvantage to the subject.

Principal investigator/sub-investigator shall record the date of and reason for withdrawal in EDC. Also, for the traceable subjects, their clinical courses are followed up and reported to the Study Secretariat. Subjects withdrawn from this study do not need to be replaced regardless of the reason for withdrawal.

- 1) Subject wishes to discontinue his/her study treatment
- 2) Subject wishes to withdraw his/her consent
- 3) Serious (or significant) AE occurs, and the study treatment is determined to be difficult to continue
- 4) A comorbidity (complication, etc.) exacerbates, and the study treatment is determined to be difficult to continue
- 5) Definitive exacerbation of RA is confirmed
- 6) Use of bDMARDs other than ADA or use of JAK inhibitor
- 7) MTX at a dosage  $\geq 10$  mg/week cannot be maintained at Week 24 due to ADR, etc.
- 8) MTX at a specified dosage (ARM-2: 10 to 25 mg/week [the maximum dose should be set according to the package insert of each country], ARM-3: 6 to 8 mg/week) cannot be maintained after Week 24 due to ADR, etc.
- 9) An increased dosage of MTX is required after Week 24 due to loss of efficacy, etc.
- 10) Confirmed pregnancy
- 11) Confirmed critical protocol deviation
- 12) Found to be applicable to an exclusion criterion after enrollment in the study
- 13) Other reasons by which the study is not appropriate for continuation as judged by principal investigator/sub-investigator

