## 6 Study treatment

#### 6.1 Treatment procedure

Subjects who fulfill the above inclusion criteria, do not meet any of the exclusion criteria, will start receiving MTX 6 to 8 mg/week after completing assessments at Week 0. Also, 10 mg of folic acid will be orally administered once a week 48 hours after the first MTX dosing day of the week to prevent ADRs related to MTX (A daily dosage of 1 mg folic acid is acceptable in South Korea on a condition that the dosage cannot be changed during the study period).

To achieve remission, the dosage of MTX will be promptly escalated to the maximum tolerable dose (MTD)  $\leq$ 25 mg/week (the maximum dose should be set according to the package insert of each country) in line with EULAR Recommendations 2016, and will be in principle maintained at the MTD from Week 12 onward. Also, the dosage of MTX will

remain unchanged from Week 20 to 24 except for dose reduction/interruption due to an ADR. Weekly dose of MTX will be administered orally at once or twice a day in principle. If the dosage of MTX is maintained  $\geq 10$  mg/week and SDAI remission is achieved at Week

24, the MTX therapy will be continued until Week 48 (ARM-1).

If SDAI remission is not achieved despite the maintenance of  $\geq 10$  mg/week MTX dose at Week 24, ADA 40 mg will be administered subcutaneously every other week until Week 48. Subjects then will be stratified by countries (Japan, South Korea, and Taiwan) as a stratification factor, and for each stratum, subjects will be randomized at a 1:1 ratio to either a group in which the MTD of MTX (10 to 25 mg/week) will be maintained (ARM-2), and a group in which the dosage of MTX will be reduced to 6 to 8 mg/week (ARM-3).

The MTX dosage shall be either 6 mg/week or 7.5 mg/week in subjects in ARM-3 whose maintenance dose of MTX at Week 24 is 10 mg/week.

Subjects in whom MTX at a dosage  $\geq 10$  mg/week cannot be maintained at Week 24 due to ADR, etc. will be withdrawn from the study.

Subjects in whom MTX at a dosage of  $\geq 10$  mg/week in ARM-2 or  $\geq 6$  mg/week in ARM-3 cannot be maintained after Week 24 due to ADR, etc. will also be withdrawn from the study. Also, subjects will be withdrawn from the study when an increased dosage of MTX is required after Week 24 due to loss of efficacy, etc.

The dose status of MTX, folic acid, and ADA, as well as the treatment groups in Week 24 onward (ARM-1 to -3) should be recorded in EDC.

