## 6.2.2 Prohibited concomitant therapy

DMARDs other than MTX and ADA are prohibited during the study. Concomitant use of Hydroxychloroquine in South Korea and Taiwan is acceptable, on condition that in principle the dosage should not change between Week 24 and 48. Subjects receiving a non-ADA bDMARD or JAK inhibitor will be withdrawn from the study immediately upon the start of such treatment.

Concomitant use of opioid analgesics except for Tramadol is prohibited in this study. Although the use of Tramadol is possible, when used it should be administered except for 3 days prior to the efficacy assessment.

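### After Week 24, a retained subject given hydroxychloroquine, another conventional DMARD or more ADA is scored on observed SDAI in the primary analysis, while a needed MTX increase normally counts as non-remission

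*Protocol*

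**What the plan says.** **What forces withdrawal.** Protocol 5.3 lists "Use of bDMARDs other than ADA or use of JAK inhibitor" (criterion 6) and a required MTX increase after Week 24 (criterion 9). Section 6.2.2 repeats the first: "Subjects receiving a non-ADA bDMARD or JAK inhibitor will be withdrawn from the study immediately upon the start of such treatment". Section 6.1 repeats the second: "subjects will be withdrawn from the study when an increased dosage of MTX is required after Week 24 due to loss of efficacy".

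**What leaves withdrawal to judgement.** Criterion 5 is "Definitive exacerbation of RA is confirmed", criterion 11 is "Confirmed critical protocol deviation", and criterion 13 covers other reasons the investigator finds sufficient. The Protocol does not define a critical deviation.

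**What is said about the other routes.**
- Section 6.2.2: "DMARDs other than MTX and ADA are prohibited during the study". Immediate withdrawal is attached only to non-ADA biologics and JAK inhibitors.
- Hydroxychloroquine in South Korea and Taiwan is "acceptable, on condition that in principle the dosage should not change between Week 24 and 48". No consequence of a change is given.
- Section 6.1: "ADA 40 mg will be administered subcutaneously every other week until Week 48". No consequence of escalation is given.

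**How Week 48 is scored.** Protocol 9.6 and SAP 2.4 make a subject a non-responder only when the assessment is missing. The mFAS (SAP 3.1.1) neither excludes nor re-scores anyone for added therapy. The PPS (SAP 3.1.2) removes deviators on prohibited therapy, but it is supplementary. SAP 2.3 provides an arm-masked data handling meeting before lock and states no rule for these cases.

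**The concern.** The trial asks whether MTX can be cut without losing remissions. Remission reached only after another RA treatment was added or ADA was increased does not show that reduced MTX with standard ADA was enough. The plan already accepts this logic for MTX, biologics and JAK inhibitors, because those subjects leave and normally count as failures. For the remaining routes the result depends on whether someone withdraws the subject.

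The trial is open-label (Protocol 4.3.2). If investigators add treatment more often in ARM-3 because they doubt the reduced dose, the resulting remissions are credited to ARM-3 and the comparison moves towards non-inferiority.

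**Working it through.** **1. Tracing each change through the rules**

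| Change after Week 24 | Status | Withdrawal | Week 48 score in mFAS |
|---|---|---|---|
| MTX increase needed | Criterion 9, section 6.1 | Required | Normally missing, so non-remission |
| Non-ADA biologic or JAK inhibitor | Criterion 6, section 6.2.2 | Required | Normally missing, so non-remission |
| Other conventional DMARD, or hydroxychloroquine in Japan | Prohibited | By judgement | Observed SDAI if retained |
| Hydroxychloroquine started or raised, South Korea or Taiwan | Arguably breaches the 6.2.2 condition | By judgement | Observed SDAI if retained |
| ADA above 40 mg every other week | Departs from 6.1 | By judgement | Observed SDAI if retained |

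The word 'normally' is needed because an early-termination assessment could fall inside the two-week window around Week 48 (Protocol 7.5).

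**2. Inputs**

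From Protocol 9.2.1.1, 9.3 and 9.4.1: 110 per arm, 30% remission in ARM-2, margin -15 points, two-sided 90% interval. Assumed, because the documents do not give them: frequency of added therapy, remission after it, and country split. Every intensified subject is taken as otherwise a non-remitter and as not withdrawn.

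**3. The plan's own figure**

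Power at 30% v 30% = Φ(0.15/√(0.42/110) - 1.645) = 78.3%. Exact enumeration over all pairs of counts gives 78.8%. Both are close to the stated 80%.

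**4. False non-inferiority with ARM-3 at the margin**

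Non-inferiority is declared if (p3 - p2) - 1.645·√{[p3(1-p3) + p2(1-p2)]/110} > -0.15. With p2 = 30% and p3 = 15%, the exact probability is 5.2%.

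*Hydroxychloroquine only*, used by 10% of ARM-3 in South Korea and Taiwan and by nobody in ARM-2. Then p3 = 15% + s × 0.10 × r, where s is the share of subjects in those countries and r is remission among users.

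| r | s = 10% | 20% | 30% | 40% |
|---|---|---|---|---|
| 10% | 5.4% | 5.6% | 5.8% | 6.0% |
| 30% | 5.8% | 6.5% | 7.2% | 7.9% |

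The shift in ARM-3 runs from 0.10 × 0.10 × 0.10 = 0.1 points to 0.40 × 0.10 × 0.30 = 1.2 points, or 0.1 to 1.3 subjects out of 110.

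The planned country-stratified Mantel-Haenszel interval was simulated with 400,000 trials per setting. Per-arm strata (Japan/South Korea/Taiwan) were 98/6/6, 88/11/11 and 66/22/22, with the Sato and the Greenland-Robins variance. The base is 5.1% to 5.3%, rising to 5.4% to 8.1%.

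*All routes, share g of non-remitters in each arm:* p3 = 15% + 85% × g × r and p2 = 30% + 70% × g × r.
- g = 5%, r = 10%: 15.4% v 30.35%, giving 5.4%.
- g = 10%, r = 50%: 19.25% v 33.5%, giving 6.6%.

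The small rise arises because ARM-3 at the margin has more non-remitters (85% v 70%).

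*All routes, equal share of each arm* (2% to 10%, r = 10% to 50%): 5.1% to 5.2%.

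**The case against.** The strongest reply is that little is left uncovered.

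- **Existing safeguards.** Inclusion criterion 6 screens out patients judged to need other DMARDs (hydroxychloroquine in South Korea and Taiwan excepted). Criteria 5, 11 and 13 can remove a subject given extra treatment for worsening RA. The masked meeting can settle single cases, and the PPS drops prohibited-therapy deviators. This stands as a reason why the gap is small. None of it states how a retained subject is scored in mFAS, and the PPS list does not clearly catch ADA escalation or a changed hydroxychloroquine dose.
- **Hydroxychloroquine is not simply permitted.** A start or increase after Week 24 arguably breaks the condition in 6.2.2 in South Korea and Taiwan too. This stands, although the qualifier in that sentence softens the condition.
- **MTX is a special case.** Raising MTX in ARM-3 moves the subject towards ARM-2 and erodes the randomised contrast, whereas hydroxychloroquine does not. That is fair, but it does not explain why a non-ADA biologic or a JAK inhibitor also ends in failure.
- **The End of Study analysis.** SAP 2.4 and 6.1 replace a missing final visit with End of Study data as a sensitivity analysis, which probes the scoring of MTX-increase withdrawals. It does not re-score added therapy.
- **Opposite bias.** With arms known, investigators may add treatment sooner in ARM-3, and a failure rule would turn that belief into ARM-3 non-remissions. This stands and is counted as a cost of the fix.

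A reader might infer that the plan allows free rescue, or that the false-positive risk could be several times the nominal 5%. The documents support neither. Most routes are deviations, and a large inflation needs widespread use across ARM-3 in all countries, none in ARM-2 and no withdrawals. Nothing in the Protocol or SAP points to that.

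**Conclusion.** The point holds as a minor one. Observed-SDAI scoring of retained, intensified subjects follows from the text. It is inconsistent with the failure that the plan normally assigns after an MTX increase, another biologic or a JAK inhibitor.

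Its size cannot be known from the documents. Under the stated assumptions, false non-inferiority moves from 5.2% to at most about 8% with one-sided hydroxychloroquine use in two countries. It moves to 5.4% to 6.6% when similar shares of non-remitters are intensified, and hardly at all when equal shares of each arm are. Confidence is medium: the reading of the rules is firm, but the frequency and arm balance of such use are assumed.

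**What to change.** Add to SAP 2.4 and 6.1 a rule of this content:

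- Any ARM-2 or ARM-3 subject is a Week 48 non-remitter in mFAS if, between the Week 24 visit and the Week 48 SDAI, the subject starts or increases hydroxychloroquine for RA, receives any other non-study DMARD for RA, or has a prescribed ADA escalation above 40 mg every other week.
- Hydroxychloroquine unchanged since before Week 24, courses for other indications and isolated ADA dosing errors do not count.
- These subjects are flagged with arm masked at the data handling meeting before lock.
- The observed-SDAI result is reported as a sensitivity analysis.
- A further sensitivity analysis also scores RA-indicated increases in oral corticosteroid as non-remission, because Protocol 6.2.1 fixes that dose with the same soft qualifier.
- The PPS stays as it is, and the rule is recorded in SAP 9.1 because it extends Protocol 9.6.

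**Cost.** SAP wording, one derived flag and two sensitivity tables. RA drug doses and ADA dose status are already recorded in EDC (Protocol 6.2, 6.1), and Protocol 4.9 covers the reasons for concomitant therapy and for dose changes.

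Remission rates fall slightly. Exact power at 30% v 30% is 79%. It becomes about 78% to 73% if ARM-3 alone loses 0.1 to 1.2 points, and stays at 79% to 80% if both arms lose the same amount, up to 1.5 points. If investigators add therapy sooner in ARM-3, the rule biases against ARM-3. That is conservative for non-inferiority, and the observed-SDAI analysis would show it.
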